8.3.5. Pregnancy in Female Partners of Male Patients

The male patient should report a pregnancy in his female partner.

Details of all partner pregnancies in female partners who become pregnant (estimated date of conception) during the study or within 2 weeks after the last dose of relugolix 120 mg or 3 months after the last dose of leuprolide acetate 22.5 mg 3-M or 6 months after the last 45 mg 6-M depot injection will be collected after the start of study intervention if the female partner agrees to provide information through a Release of Information form.

If a partner pregnancy is reported, the investigator should inform the sponsor (or designee) within 8 calendar days of learning of the pregnancy and should follow the procedures outlined in [Appendix 3](#).

Protocol Amendment 2

Abnormal pregnancy outcomes (eg, spontaneous abortion, fetal death, stillbirth, congenital anomalies, ectopic pregnancy) are considered serious adverse events.

8.3.6. Safety Management Plan

Further detailed information on reporting of serious adverse events and nonserious adverse events leading to treatment discontinuation is included in the safety management plan. The safety management plan shall set forth rules and procedures concerning pharmacovigilance reporting and shall supersede all prior pharmacovigilance and safety agreements.

The CRO will not monitor the sponsor's regulatory reporting obligations to the Health Authorities.

8.4. Treatment of Overdose

An overdose is defined as a known deliberate or accidental administration of study intervention, to or by a study patient, at a dose above that assigned to that individual patient according to relugolix labelling.

For this study, any dose of relugolix greater than the daily dose of relugolix 120 mg following the 360-mg loading dose, or 240 mg per day as part of dose modification when relugolix is combined with P-gp and strong CYP3A inducers, will be considered an overdose. There is no known antidote for an overdose.

Refer to product labelling for leuprolide acetate in the event of an overdose.

The investigator reports overdose events to the CRO within 8 calendar days of awareness; the CRO reports overdoses to the sponsor (or designee) with 5 days of awareness, respectively, according to [Appendix 2](#), whether or not the overdose is associated with an adverse event.

The quantity of the excess dose as well as the duration of the overdose should be documented in the Overdose electronic case report form (eCRF).

Decisions regarding dose interruptions or modifications will be made by the investigator in consultation with the medical monitor based on the clinical evaluation of the patient.

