4.3. Justification for Dose

The recommended dosing regimen for relugolix is a single 360-mg loading dose (3×120 -mg tablets) taken orally, followed by a 120-mg dose (1×120 -mg tablet), taken orally, once daily; in the event that in addition to the relugolix the patient requires a combined P-glycoprotein (P-gp) inducer and strong CYP3A inducer, relugolix dosing will be the same single 360 mg loading dose followed by 240 mg dose daily ([ORGOVYX \[relugolix\] USPI 2023](#)). Leuprolide acetate 3-M or 6-M depot injection (per the investigator's judgement) was selected as the active comparator.

As of 04 Dec 2023, patients currently enrolled in this study will be provided with up to a 12-month clinical supply of the randomized study intervention (relugolix or leuprolide acetate) they had been previously assigned. This clinical supply is intended to mitigate any interruptions in treatment and to allow sufficient time for patients to transition from study treatment to SOC by their health care providers as soon as practicable.

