6.5.3. Prohibited Medications

Co-administration of relugolix 120 mg with oral P-gp inhibitors should be avoided. If co-administration is unavoidable, relugolix 120 mg should be taken first, then wait at least 6 hours before taking the P-gp inhibitor ([ORGOVYX \(relugolix\) USPI 2023](#)). Treatment with relugolix 120 mg may be interrupted for up to two weeks if a short course of treatment with a P-gp inhibitor is required. If treatment with relugolix is interrupted for more than 7 days, resume administration of relugolix with a 360 mg loading dose on the first day, followed by 120 mg once daily.

If co-administration with combined P-gp and strong CYP3A inducers is unavoidable, increase the relugolix dose to 240 mg once daily. After discontinuation of the combined P-gp and strong CYP3A inducer, resume the recommended dose of 120 mg relugolix once daily ([ORGOVYX \(relugolix\) USPI 2023](#)).

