7. PATIENT DISCONTINUATION/WITHDRAWAL

7.1.1. Temporary Discontinuation

At the discretion of the investigator, study drug can be held for a period of up to 14 consecutive days for evaluation and treatment of an adverse event. Patients may be rechallenged per the investigator's discretion, ending Dec 2024. If treatment with relugolix is interrupted for more than 7 days, resume administration of relugolix with a 360 mg loading dose on the first day, followed by 120 mg once daily. Active sites will receive clinical drug supply until all patients transition to SOC.

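### The relugolix restart rule does not say how it applies to a patient still on a combined inducer, and the overdose definition is silent on a repeat loading dose

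*Protocol*

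**What the plan says.** **Starting regimen.** Protocol 4.3 says: "The recommended dosing regimen for relugolix is a single 360-mg loading dose". A daily dose of 120 mg follows. Sections 6.1 and 6.3 place the loading dose on Day 1.

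**With a combined P-gp and strong CYP3A inducer.** Section 4.3 says "relugolix dosing will be the same single 360 mg loading dose followed by 240 mg dose daily". Section 6.5.3 says "If co-administration with combined P-gp and strong CYP3A inducers is unavoidable, increase the relugolix dose to 240 mg once daily", and has the patient go back to 120 mg once the inducer is stopped. Section 6.5.1 permits apalutamide. Section 6.6 identifies it as an inducer of this kind and refers the reader to 6.5.3.

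**Restart.** Under 7.1.1, for an adverse event, "study drug can be held for a period of up to 14 consecutive days". If the gap exceeds 7 days, the site is to "resume administration of relugolix with a 360 mg loading dose on the first day, followed by 120 mg once daily". Section 6.5.3 gives the same instruction in its paragraph on P-gp inhibitors, where an interruption of up to two weeks is allowed. Neither place mentions inducers.

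**Overdose.** Section 8.4 first defines overdose as administration "at a dose above that assigned to that individual patient according to relugolix labelling". It then sets a study-specific limit, "any dose of relugolix greater than the daily dose of relugolix 120 mg following the 360-mg loading dose", and makes an allowance for 240 mg per day when an inducer is used. A second loading dose is not mentioned.

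**The concern.** Two places in the dosing text do not join up.

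- **Restart and inducer rules.** A site that follows 7.1.1 literally for a patient still on apalutamide reaches a daily dose that differs from the protocol's own inducer rule. Amendment 2 keeps patients on relugolix for up to 12 months, so this text is in use for people under treatment.
- **Restart and overdose definition.** A site that takes the loading dose in 8.4 to mean only the Day 1 dose could record a restart directed by the protocol as an overdose, while another site would not. Overdoses must be reported whether or not an adverse event occurs, and the amount of the excess goes into a dedicated eCRF. The same event could therefore be recorded in two ways, in a study whose one remaining objective is to describe the safety of relugolix.

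**Working it through.** No alpha, power, event count or sample size is involved, and the plan gives no figure to reproduce. The check is a comparison of passages and simple dose arithmetic.

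**Step 1: when the restart rule applies.** The trigger is more than 7 days off drug (6.5.3, 7.1.1). The longest adverse event hold is 14 consecutive days (7.1.1). Permitted holds of 8 to 14 days therefore trigger the rule.

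**Step 2: a patient still on a combined inducer who restarts after such a hold.**

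| Text | First day | Daily dose after that |
|---|---|---|
| Restart rule, 6.5.3 and 7.1.1 | 360 mg | 120 mg |
| Inducer regimen, 4.3 | 360 mg | 240 mg |
| Inducer paragraph, 6.5.3 | not stated | 240 mg |

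- Sections 4.3 and 7.1.1 agree on the first-day dose.
- The daily doses differ: 240 / 120 = 2.
- Section 6.5.3 ties the return to 120 mg to stopping the inducer. This patient has not stopped it.
- Section 8.4 does not settle the matter. With an inducer, neither 120 mg nor 240 mg per day exceeds its limit.

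**Step 3: the restart dose against 8.4.** The result depends on what the loading dose in 8.4 covers.

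- *Narrow reading, Day 1 only.* Without an inducer, 360 / 120 = 3, an excess of 360 − 120 = 240 mg. With an inducer, 360 / 240 = 1.5, an excess of 360 − 240 = 120 mg. The restart would be recorded as an overdose.
- *Broad reading, any loading dose the protocol directs.* A restart at 360 mg followed by 120 mg fits the definition. There is no overdose and nothing to enter.

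For the narrow reading: 4.3 calls the loading dose single, 6.1 and 6.3 put it on Day 1, and the inducer allowance in 8.4 has no loading-dose clause of its own. For the broad reading: 6.5.3 and 7.1.1 themselves call the restart dose a loading dose, and the opening of 8.4 refers to the dose assigned to the individual patient.

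**Step 4: where a misread restart would appear.** Under 8.4 the investigator reports an overdose to the CRO within 8 calendar days, and the CRO reports to the sponsor within 5 days. Appendix 2 says that overdose in itself is not an adverse event or serious adverse event unless it is intentional with possible self-harm intent. None of the tables named in SAP 6.1 is an overdose table, although that list is not exhaustive. The effect therefore falls on overdose reports and eCRF entries, not on the named adverse event tables.

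**The case against.** The strongest reply is that this is ordinary drafting, with a general rule in one place and a special case in another. There is only one restart instruction, stated twice in the same terms. The inducer text does not mention restarting, and 6.6 sends apalutamide users to 6.5.3, where the inducer paragraph comes directly after the restart sentence. Section 8.4 also has dose decisions made with the medical monitor. As for overdose, a dose that the protocol directs for a patient is hard to call higher than the one assigned to him. The study is in wind-down, limited to December 2024.

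Part of this stands. A reader might infer that the restart, inducer and overdose rules all contradict one another. They do not, because 8.4 expressly allows 240 mg with an inducer. Nor are there two competing restart instructions.

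The reply does not remove the first gap. Section 7.1.1 repeats the restart rule on its own, for adverse event holds, with no exception and no reference back to 6.5.3. Nothing in the protocol says which text prevails for a patient still on an inducer. Consulting the medical monitor lowers the risk but leaves the text unresolved.

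**Conclusion.** The point holds in two parts of unequal weight.

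1. **Restart and inducer rules: a real inconsistency.** For a patient still on a combined inducer who restarts after more than 7 days off, the protocol's texts differ two-fold in daily dose (120 mg against 240 mg). The case is foreseeable, because apalutamide is permitted and holds of 8 to 14 days are allowed. Which dose is right is not judged here.

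2. **Restart and overdose definition: an ambiguity.** Section 8.4 supports two readings of the same restart, one giving a recorded excess of 240 mg (120 mg with an inducer) and the other giving none.

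Two stronger conclusions are tempting and are not supported. One is that every interruption of more than 7 days ends in a recorded overdose; that needs the narrow reading and sets aside the opening sentence of 8.4. The other is that the safety results would be distorted; Appendix 2 keeps overdose in itself out of the adverse event data except in the self-harm case, and SAP 6.1 names no overdose summary.

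The documents do not give the number of patients on an inducer, the number of long holds, or whether any overdose has been recorded. The size in patients is therefore unknown and may be small. Correction is still worthwhile, because the text directs dosing for patients under treatment.

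**What to change.** The clinical team should reconcile Protocol 4.3, 6.5.3, 7.1.1 and 8.4 so that:

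- the restart rule, in both places, states its scope for a patient still on a combined P-gp and strong CYP3A inducer;
- 8.4 states whether doses directed by 4.3, 6.5.3 or 7.1.1, including a repeat loading dose, count as overdose.

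The reconciled definition should then go into the completion instructions for the Overdose eCRF, and any overdose records already entered should be reviewed against it.

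The cost is a protocol clarification, an eCRF completion note and a check of whatever overdose records exist. The planned analyses do not change.

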8.5. Pharmacokinetics

Pharmacokinetic parameters are not evaluated in this study.

8.6. Pharmacodynamics

Pharmacodynamic parameters are not evaluated in this study.

8.7. Genetics

Genetics are not evaluated in this study.

8.8. Biomarkers

Biomarkers are not evaluated in this study.

8.9. Immunogenicity Assessments

Immunogenicity will not be evaluated in this study.

9. STATISTICAL CONSIDERATIONS

9.1. Statistical Hypotheses

No formal primary and secondary analysis for this study will be performed.

9.2. Analysis Populations

Safety population is defined as all randomized patients who are treated with at least one dose of relugolix or one injection of leuprolide acetate after the date of randomization to the study.

Safety population will be used to analyze other safety data including treatment-emergent adverse events and clinical laboratory tests as obtained per standard of care.

9.3. Statistical Analyses

The statistical analysis plan will be finalized prior to database lock and it will include a more technical and detailed description of the statistical analyses described in this section. The adverse event analysis will be elaborated in the statistical analysis plan, all other baseline data will be collected and will be listed.

9.3.1. General Considerations

All statistical analyses will be conducted using SAS® Version 9.4 or higher.

10. SUPPORTING DOCUMENTATION AND OPERATIONAL CONSIDERATIONS

APPENDIX 1. REGULATORY, ETHICAL, AND STUDY OVERSIGHT CONSIDERATIONS

Regulatory and Ethical Considerations

- This study will be conducted in accordance with the protocol and with the following:
 - Consensus ethical principles derived from international guidelines including the Declaration of Helsinki and Council for International Organizations of Medical Sciences (CIOMS) International Ethical Guidelines
 - Applicable International Council for Harmonization of Technical Requirements for Pharmaceuticals for Human Use (ICH) Good Clinical Practice (GCP) Guidelines
 - Applicable laws and regulations
- The protocol, protocol amendments, ICF, Investigator Brochure, and other relevant documents (eg, advertisements) must be submitted to an IRB/IEC by the investigator and reviewed and approved by the investigational review board (IRB)/independent ethics committee (IEC) before the study is initiated.
- Any amendments to the protocol will require IRB/IEC approval before implementation of changes made to the study design, except for changes necessary to eliminate an immediate hazard to study patients.
- The investigator will be responsible for the following:
 - Providing written summaries of the status of the study to the IRB/IEC annually or more frequently in accordance with the requirements, policies, and procedures established by the IRB/IEC
 - Notifying the IRB/IEC of serious adverse events or other significant safety findings as required by IRB/IEC procedures
 - Providing oversight of the conduct of the study at the site and adherence to requirements of 21 Code of Federal Regulations (CFR), ICH guidelines, the IRB/IEC, European regulation 536/2014 for clinical studies (if applicable), and all other applicable local regulations

Financial Disclosure

Investigators and sub-investigators will provide the Sponsor with sufficient, accurate financial information as requested to allow the Sponsor to submit complete and accurate financial certification or disclosure statements to the appropriate regulatory authorities. Investigators are responsible for providing information on financial interests during the course of the study and for 1 year after completion of the study.

Informed Consent Process

- The investigator or his/her representative will explain the nature of the study to the patient or his/her legally authorized representative and answer all questions regarding the study.

Protocol Amendment 2

- Patients must be informed that their participation is voluntary. Patients will be required to sign a statement of informed consent that meets the requirements of 21 CFR 50, local regulations, ICH guidelines, Health Insurance Portability and Accountability Act requirements, where applicable, and the IRB/IEC or study center.
- Patients can sign a paper ICF to be eligible for the discontinuation phase of the study. Electronic informed consent (eConsent) will not be available.
- The medical record must include a statement that written informed consent was obtained to allow the patient to continue in the discontinuation phase and the date the written consent was obtained. The authorized person obtaining the informed consent must also sign the ICF.
- Patients must be re-consented to the most current version of the ICF(s) during their participation in the study. Re-consent must occur through the paper ICF consent.
- A copy of the paper ICF(s) must be provided to the patient and the patient's legally authorized representative and the investigator will maintain the signed original document within the patient's record file per local requirements.
- For patients who consented to prior versions of the protocol via eConsent, a copy of the electronic ICF(s) will be available to the patient to review and print a copy via the secure portal.
- The investigator will also fully document the informed consent process in the patient's source records.
- Due to the study entering into a discontinuation phase, all enrolled patients will need to be reconsented.

Data Protection

- Patients will be assigned a unique identifier by the sponsor. Any patient records or datasets that are transferred to the sponsor will contain the identifier only; patient names or any information which would make the patient identifiable will not be transferred.
- The patient must be informed that his personal study-related data will be used by the sponsor in accordance with local data protection law. The level of disclosure must also be explained to the patient who will be required to give consent for their data to be used as described in the informed consent
- The patient must be informed that his medical records may be examined by Clinical Quality Assurance auditors or other authorized personnel appointed by the sponsor, by appropriate IRB/IEC members, and by inspectors from regulatory authorities.

Dissemination of Clinical Study Data

Study information from this protocol will be posted on publicly available clinical trial registers before enrollment of patients begins. Results will be posted as per local country requirements.

Data Quality Assurance

This study will be monitored by the sponsor (or designee) in accordance with current GCP regulations. By signing this protocol, the investigator grants permission to Sumitomo Pharma Switzerland GmbH (or designee) and appropriate regulatory authorities to conduct on-site monitoring of all appropriate study documentation. In order to assure the accuracy of data collected in the eCRF, it is mandatory that representatives of the sponsor (or designee) have access to original source documents (eg, patient records, patient charts, hospital records and laboratory reports).

During the review of these documents, the anonymity of the patient will be respected with strict adherence to professional standards of confidentiality. The CRO monitor will contact the site regularly and will be allowed, on request at a mutually acceptable time, to inspect the various records of the study. It will be the study monitor's responsibility to inspect the eCRF at regular intervals throughout the study, to verify the adherence to the protocol and the completeness, correctness, and accuracy of all eCRF entries, and to meet with the investigator to discuss study progress and compliance with the protocol and GCPs. The study monitor should have access to any source records and data needed to verify the entries on the eCRF. The investigator agrees to cooperate with the study monitor to ensure that any problems detected in the course of these monitoring visits are resolved. For this study, patient data will be entered into an electronic database and combined with data provided from other sources in datasets then transmitted electronically to the sponsor (or designee).

Management of clinical data will be performed in accordance with applicable sponsor-approved standards and data cleaning procedures to ensure the integrity of the data (eg, removing errors and inconsistencies in the data).

The intensity, frequency and scope of monitoring activities will be proportionate to the risks identified during the risk-assessment and ensure that study patient safety and rights are upheld, and data is of high quality. Centralized and remote monitoring is utilized in preference to site-based monitoring when appropriate and feasible.

Following the risk assessment, identified risks will be triaged and a study-specific monitoring plan will be developed. Standard centralized monitoring procedures for data quality will include programming of automatic error and plausibility checks within the ePRO sent to study patients. In addition, a variety of checks will be implemented within the central database. Monitoring will focus on patient safety and rights (conforming with regulatory requirements, informed consent) and source data verification.

Serious adverse events and concomitant medications terms will be coded using the Medical Dictionary for Regulatory Activities and the World Health Organization Drug Dictionary Enhanced, respectively.

The CRO will retain original source documents and the sponsor will receive eCRF required data as electronic datasets. Patient initials will not be collected or transmitted to the sponsor.

Records and documents pertaining to the conduct of this study must be retained by the CRO for 2 years after study completion unless local regulations or institutional policies require a longer retention period. No records may be destroyed during the retention period without the written

Protocol Amendment 2

approval of the sponsor. No records may be transferred to another location or party without written notification to the sponsor.

Source Documents

- Source documents provide evidence for the existence of the patient and substantiate the integrity of the data collected.
- Data reported on the CRF or entered in the eCRF that are transcribed from source documents must be consistent with the source documents or the discrepancies must be explained. The CRO may need to request previous medical records or transfer records, depending on the study. Also, current medical records must be available.
- Definition of what constitutes source data can be found in the Site Monitoring Plan.

Publication Policy

- The results of this study may be published or presented at scientific meetings. If this is foreseen, the investigator agrees to submit all manuscripts or abstracts to the sponsor before submission. This allows the sponsor to protect proprietary information and to provide comments.
- The sponsor will comply with the requirements for publication of study results. In accordance with standard editorial and ethical practice, the sponsor will generally support publication of multicenter studies only in their entirety and not as individual site data. In this case, a coordinating investigator will be designated by mutual agreement.
- Authorship will be determined by mutual agreement and in line with International Committee of Medical Journal Editors authorship requirements.

APPENDIX 2. ADVERSE EVENTS: DEFINITIONS AND PROCEDURES FOR RECORDING, EVALUATING, FOLLOW-UP, AND REPORTING

Definition of Adverse Events

Adverse Events Definition

An adverse event is any untoward medical occurrence in a patient or clinical study participant, temporally associated with the use of study intervention, whether or not considered related to the study intervention.NOTE: An adverse event can therefore be any unfavorable and unintended sign (including an abnormal laboratory finding), symptom, or disease (new or exacerbated) temporally associated with the use of study intervention.

Events Meeting the Adverse Event Definition

Any abnormal laboratory test results (hematology, clinical chemistry, or urinalysis) or other safety assessments (eg, ECG, radiological scans, vital signs measurements), including those that worsen from baseline, considered clinically significant in the medical and scientific judgment of the investigator (ie, not related to progression of underlying disease).Exacerbation of a chronic or intermittent pre-existing condition including either an increase in frequency and/or intensity of the condition.New conditions detected or diagnosed after study intervention administration even though it may have been present before the start of the study.Signs, symptoms, or the clinical sequelae of a suspected drug-drug interaction.Signs, symptoms, or the clinical sequelae of a suspected overdose of either study intervention or a concomitant medication. Overdose per se will not be reported as an adverse event/serious adverse event unless it is an intentional overdose taken with possible suicidal/self-harming intent. Such overdoses should be reported regardless of sequelae.The signs, symptoms, and/or clinical sequelae resulting from lack of efficacy will be reported as adverse event or serious adverse event if they fulfil the definition of an adverse event or serious adverse event. Also, “lack of efficacy” or “failure of expected pharmacological action” also constitutes an adverse event or serious adverse event.Selective safety data, including serious adverse events and nonserious adverse events leading to treatment discontinuation will be collected for this study.

Events NOT Meeting the Adverse Event Definition

Any clinically significant abnormal laboratory findings or other abnormal safety assessments which are associated with the underlying disease, unless judged by the investigator to be more severe than expected for the participant’s condition.

- The disease/disorder being studied or expected progression, signs, or symptoms of the disease/disorder being studied, unless more severe than expected for the participant's condition.
- Medical or surgical procedure (eg, endoscopy, appendectomy): the condition that leads to the procedure is the adverse event.
- Situations in which an untoward medical occurrence did not occur (social and/or convenience admission to a hospital).
- Anticipated day-to-day fluctuations of pre-existing disease(s) or condition(s) present or detected at the start of the study that do not worsen.

A serious adverse event is defined as any untoward medical occurrence that, at any dose:

a. Results in death

b. Is life-threatening

- The term 'life-threatening' in the definition of 'serious' refers to an event in which the patient was at risk of death at the time of the event. It does not refer to an event, which hypothetically might have caused death, if it were more severe.

c. Requires inpatient hospitalization or prolongation of existing hospitalization

- In general, hospitalization signifies that the patient has been detained (usually involving at least an overnight stay) at the hospital or emergency ward for observation and/or treatment that would not have been appropriate in the physician's office or outpatient setting. Complications that occur during hospitalization are adverse events. If a complication prolongs hospitalization or fulfills any other seriousness criteria, the event is serious. When in doubt as to whether "hospitalization" occurred or was necessary, the adverse event should be considered serious.
- Hospitalization for elective treatment of a pre-existing condition that did not worsen from baseline is not considered an adverse event.

d. Results in persistent disability/incapacity

- The term disability means a substantial disruption of a person's ability to conduct normal life functions.
- This definition is not intended to include experiences of relatively minor medical significance such as uncomplicated headache, nausea, vomiting, diarrhea, influenza, and accidental trauma (eg, sprained ankle) which may interfere with or prevent everyday life functions but do not constitute a substantial disruption.

e. Is a congenital anomaly/birth defect

f. Other situations:

- Medical or scientific judgement should be exercised in deciding whether serious adverse event reporting is appropriate in other situations such as important medical events that may not be immediately life-threatening or result in death or hospitalization but may jeopardize the patient

or may require medical or surgical intervention to prevent one of the other outcomes listed in the above definition. These events should usually be considered serious.

- Examples of such events include invasive or malignant cancers, intensive treatment in an emergency room or at home for allergic bronchospasm, blood dyscrasias or convulsions that do not result in hospitalization, or development of drug dependency or drug abuse.

Recording and Follow-Up of Adverse Events and Serious Adverse Events by the CRO

Adverse Event and Serious Adverse Event Recording

- Adverse events and serious adverse events will be reported by the patient (or, when appropriate, by a caregiver, surrogate, or the patient's legally authorized representative) using questionnaires. The CRO is responsible for checking the questionnaires for selective safety data (ie, serious adverse events and nonserious adverse events leading to treatment discontinuation) and for recording, reporting, and following up of these events. Serious adverse events and nonserious adverse events leading to discontinuation of relugolix or leuprolide acetate will also be reported directly by the principal investigator.
- The report will be assessed for seriousness and causal relationship to the study intervention by the CRO.
- Reports meeting the minimum criteria for reporting, that are assessed as serious, will be sent to the sponsor as a source record with all available information within 5 calendar days of CRO awareness of the information (unless there are unexpected fatal or life-threatening suspected adverse reaction reports in which case they will be reported to the sponsor or designee within 2 business/3 calendar days, whichever is shorter), with the Day 0 as the date the record is electronically received by the CRO. If new information about the case is gained in the process of case validation or follow-up, ie, after contacting the patient and/or physician, the follow-up source will be sent to the sponsor within 5 calendar days of receipt of the new information unless there are unexpected fatal or life-threatening suspected adverse reaction reports in which case they will be reported to the sponsor or designee within 2 business/3 calendar days, whichever is shorter.
- The CRO will record all relevant serious adverse event and nonserious adverse event leading to treatment discontinuation data in the eCRF.
- There may be instances when copies of medical records for certain cases are requested by the sponsor or their representative. In this case, all patient identifiers, with the exception of the patient number, will be redacted on the copies of the medical records before submission.
- The CRO will attempt to confirm a diagnosis of the event based on signs, symptoms, and/or other clinical information. Whenever possible, the diagnosis (not the individual signs/symptoms) will be documented as a serious adverse event.
- All overdose events are to be reported within 5 calendar days of awareness by the CRO to the sponsor (or designee), whether or not the overdose is associated with an adverse event.

Assessment of Severity

For selective safety data not submitted directly by the investigator (with investigator assessment of severity), the CRO will make an assessment of severity for each serious adverse event and nonserious

Protocol Amendment 2

adverse event leading to treatment discontinuation reported during the treatment period according to the National Cancer Institute's Common Terminology Criteria for Adverse Events (CTCAE) using the available information. For diseases not specified with the CTCAE, the criteria below should be used to determine the grade severity:

Severity Grade	Criteria
1/Mild	Asymptomatic or mild symptoms, clinical or diagnostic observations only; intervention not indicated
2/Moderate	Minimal, local, or noninvasive intervention indicated; limiting age-appropriate instrumental activities of daily living
3/Severe or Medically Significant	Not immediately life-threatening; hospitalization or prolongation of hospitalization indicated; disabling; limiting self-care activities of daily living
4/Life-Threatening	Life-threatening consequences; urgent intervention indicated
5/Death	Death related to adverse event

Note: An event is defined as 'serious' when it meets at least one of the predefined outcomes as described in the definition of a serious adverse event, NOT when it is rated as severe.

Assessment of Causality

For selective safety data not submitted directly by the investigator (with investigator assessment of causality), the CRO is obligated to assess the relationship between study intervention and each occurrence of each serious adverse event. The CRO drug safety physicians are responsible for assessing the causality.

A reasonable possibility of a relationship conveys that there are facts, evidence, and/or arguments to suggest a causal relationship, rather than a relationship cannot be ruled out.

The CRO will use clinical judgement to determine the relationship.

Alternative causes, such as underlying disease(s), concomitant therapy, and other risk factors, as well as the temporal relationship of the event to study intervention administration will be considered and investigated.

The CRO drug safety physician will also consult the relugolix investigator brochure and/or Product Information, for marketed products, in his/her assessment.

For each serious adverse event reported, the CRO drug safety physician **must** document that he/she has reviewed the adverse event and has provided an assessment of causality.

There may be situations in which a serious adverse event has occurred and the CRO has minimal information to include in the initial report. However, it is very important that the CRO always makes an assessment of causality for every event before the initial transmission of the serious adverse event report. The CRO drug safety physician may change his/her opinion of causality in light of follow-up information and send a follow-up report with the updated causality assessment.

The causality assessment is one of the criteria used when determining regulatory reporting requirements.

The following definitions are to be used for the relationship of the adverse event to study intervention:

- **Probably related:** A clinical event, including laboratory test abnormality, with a reasonable time sequence to administration of the drug, unlikely attributed to concurrent disease or other drugs or chemicals, and that follows a clinically reasonable response on readministration (rechallenge) or withdrawal (dechallenge).
- **Possibly related:** A clinical event, including laboratory test abnormality, with a reasonable time sequence to administration of the drug but that could also be explained by concurrent disease or other drugs or chemicals. Information on drug withdrawal may be lacking or unclear.
- **Not related:** A clinical event, including laboratory test abnormality, with a temporal relationship to drug administration that makes a causal relationship improbable and/or in which other drugs, chemicals, or underlying disease provide a plausible explanation.

Follow-up of Serious Adverse Events

- All serious adverse events will be followed until resolution, stabilization, the event is otherwise explained, or the patient is lost to follow-up (as defined in Section 7.3).
- If a patient dies during participation in the study or during a recognized follow-up period, the investigator will provide the sponsor with a copy of any postmortem findings including histopathology, if available.
- New or updated information will be recorded in the originally completed CRF.

The CRO will submit any updated serious adverse event data within 5 calendar days of electronic data capture. Unless there are unexpected fatal or life-threatening suspected adverse reaction reports, in which case they will be reported within 2 business/3 calendar days, whichever is shorter.

Reporting of Adverse Events and Serious Adverse Events by the Recruiting Physician**Adverse Event and Serious Adverse Event Reporting**

- Adverse events and serious adverse events may also be reported by the patient (or caregiver, surrogate, or patient's legally authorized representative) directly to the recruiting physician. If the physician becomes aware of any serious adverse events or nonserious adverse events leading to treatment discontinuation, the recruiting physician is responsible for reporting these selective safety data to the sponsor (or designee).
- E-mail transmission is the preferred method to transmit this information to the sponsor (or designee) for inclusion in the global safety database.
- All overdose events are to be reported within 8 calendar days of awareness by the recruiting physician to the sponsor (or designee), whether or not the overdose is associated with an adverse event.

The contact information for submission of serious adverse events, nonserious adverse events leading to treatment discontinuation, and events of overdose is provided on the study MVT-601-056 safety report form and in the safety management plan.

The initial report should include:

- Study number (MVT-601-056)
- Site address and number
- Investigator name
- Patient ID number, sex, and age
- Details of study intervention administration
- The date of the report
- A description of the event (event term, seriousness of the event, date of onset, severity per CTCAE)
- Causal relationship to the study intervention

